5. LIST OF ABBREVIATIONS

6. PROTOCOL SUMMARY

Full Title: Systemic Effect of Lycosome-Formulated Dark Chocolate and GA Lycopene on Gut Microbiota, Liver Metabolism, Blood Markers of Oxidative Status and Skin Parameters in Healthy Overweight Volunteers

Short Title: Effect of Lycosome-Formulated Dark Chocolate and Lycopene on Gut Microbiota, Liver, Blood and Skin

Sample Target Size: 30

Study Population: Healthy Caucasian males and females with no acute or chronic diseases aged from 50 to 70 years with body mass index more than 30 and less than 35 kg/m².

Participating Sites:

1. Lycotec Ltd, [name]. [contact] [contact]
2. Institute of Cardiology, [name], Russia

Study Design:

The study is designed as a single, interventional, randomized clinical study to determine if one month's consumption of lycosome-formulated dark chocolate (DC) containing lycopene affects the spectrum of intestinal microbiota, blood lipids, liver parameters and oxidative status of healthy volunteers. The effects of lycopene alone and DC without lycopene addition are in the scope of the control groups as secondary objectives. All volunteers will be asked to give written consent to participation in the study and will be informed about the major goal of the study and its objectives.

The major research question to be answered in the study is whether ingestion of lycosome formulated DC or its two major constituents – lycopene and cocoa flavanols for 1 month can affect the composition of the gut microbiota, liver metabolism, blood markers of biological oxidation and skin parameters in healthy middle-aged overweight individuals.

Therefore, the primary endpoint of the project will be parameters reflecting composition of gut microbiota, blood lipids and markers of serum levels of biological oxidation – malonic dialdehyde, oxidized LDL and certain other values. The secondary endpoints will be skin parameters – sebum, corneocytes and bacterial load. Each of these parameters will be measured before trial initiation ("0" time point) and after 1 month (final point of clinical study).

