The study will be conducted following enrolment of 30 volunteers with equal representation in the study population of males and females. The study is planned to include healthy overweight individuals in the age range of 50 to 70 years old, with confirmed health status and no indication of chronic or acute disease. In particular, volunteers with history or immediate signs of

liver disease, alcoholism or intake of any medication (non-steroidal anti-inflammatory drugs, hormones, vitamins and food supplements or energy drinks) will be excluded from participation in the study. Among other exclusion criteria will be pregnancy, extensive tobacco smoking (>10 cigarettes per day), and history of cardiovascular disease. To minimize inconsistencies originating from body weight, patients with Body Mass Index (BMI) from 30 to 35 will be enrolled in the study. All volunteers will be requested to withdraw from consumption of dark chocolate, cocoa and lycopene containing products (tomatoes, ketchup etc.) for 2 weeks prior to study initiation and will be requested to ingest cocoa and lycopene-containing products strictly as mandated by the study protocol.

All study participants will undergo a preliminary anamnestic and clinical investigation. This will include reading the vital signs, determination of body mass index, anthropometry, blood pressure measurement, and electrocardiography. Among the laboratory tests will be determination of fasting serum glucose and lipids (total cholesterol, LDL cholesterol, HDL and total triglyceride levels), determination of ALT and AST level, total bilirubin, and CRP. All volunteers will be also be subject to a standard hematological investigation.

The volunteers will be randomized according to age, gender, body weight and BMI using a simple randomization method and block randomization.

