The interventional procedure will be conducted stringently according to the conditions described in the protocol approved by the Institutional Review Board. In particular, volunteers will be given the study products over two separate visits for a total of one month's supply. To assess effect of lycosome-formulated DC volunteers from the first arm will be given lycosome-formulated DC containing 7mg lycopene while volunteers from the fifth arm will be given the regular formulation of DC without lycopene. Volunteers from the second arm of the study will be given capsules containing 7 mg of lycopene, this amount is equal to the amount of lycopene ingested daily with lycosome-formulated DC. Investigational products will be given to volunteers twice – at the "0" time point of the study and at the intermediate time point (two weeks after study initiation). To assess dose-dependency and effect of fat matrix volunteers from the third and fourth arms will be given 30 mg of lycopene in either cocoa butter or sunflower oil.

Upon arrival at the study site all volunteers will be asked about current health status and will undergo scrupulous anamnestic, physical and laboratory investigations. Each of these procedures will be conducted by

highly trained medical professionals including nurses and practicing physicians.

Study products will be given immediately after all evaluations are complete.

Lycosome formulation of DC is a proprietary formulation of DC (Lycotec Ltd, Cambridge, UK) with enhanced bioavailability of lycopene and cocoa flavanols in which the flavanols are protected from oxidation by a lycopene coat and embedded into cocoa butter micelles of the chocolate matrix preserving thereby cocoa flavanols from degradation and oxidation. The final concentration of lycopene in 10 grams of the composite lycosome formulation of DC is 7 mg. The lycopene is in the form of tomato oleoresin from Lycored Inc. (NJ, USA) and contains 97% all trans-isomers and 3% all cis-isomers.

Volunteers will be asked to consume the investigational products in the evening with the main meal once a day for 1 month.

Blood serum specimens will be collected, processed, aliquoted and frozen at – 80°C for later analysis at both the “0” time point of the study and after 1 month of the study. All aliquots will be coded without the name of the volunteer being indicated. The identity of specimens will be known only to the Principal Investigator and the Medical Monitor.

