7.4 Study Design

7.4.1 Selection and randomization of volunteers

Medical personnel at the outpatient clinic of Saratov Institute of Cardiology will be informed about implementing the study, its major goal and selection criteria for volunteers. Suitable individuals will be invited for preliminary check-up (physical and laboratory investigation) during the initial phase of enrolment. All suitable individuals will be re-screened after the wash-out period of the study before the final decision on study enrolment is made.

Randomization of volunteers in the study will be performed using widely accepted methods such as simple randomization and stratified randomization. Briefly, the

software containing a random number generator will be applied to the database of volunteers. The assigned group will be considered as final. The groups will be balanced according to numerical age and gender with special software. Stratified randomization will be used to enhance statistical strength of the final results and will ensure equality of groups for secondary selection criteria.

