12.2 Withdrawal of subjects due to adverse events

Any subject with adverse reaction and/or abnormal laboratory test findings will be withdrawn from the study by the Medical Officer and replaced with an eligible volunteer from the pre-screened pool of volunteers. An appropriate report to the Local Ethical Committee will be filed.

13. Statistical Methods/Data Analysis: 9.1

Study endpoint

For assessment of normally distributed parameters the Shapiro-Wilk method will be used. Student's t-test will be applied both for paired and unpaired samples. Between-group differences at one time point will be evaluated by Wilcoxon-Mann-Whitney test (continuous variables) and Fisher's Exact test (categorical variables). Data analysis will be performed using Stata SE, version 12.1. All statistical tests are two-sided and statistical significance level alpha will be set at 0.05 for the analysis.

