10.1 Statistical effectiveness analysis

Statistical analysis of results will be performed by an independent statistician. If the statistical methods as well as the statistical settings listed above are not appropriate for newly obtained results due to specificity of variant distribution, other methods of statistical analysis will be applied. Any deviations from the statistical plan described above will be explained and justified in a protocol amendment and/or in the final report submitted to the Institutional Ethics Committee.

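### Section 13 compares arms at one time point and specifies no baseline-adjusted between-arm analysis, although every endpoint is measured at month 0 and month 1

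*Protocol*

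**What the plan says.** Protocol section 13 (Study endpoint) names a Shapiro-Wilk check and then says that Student's "t-test will be applied both for paired and unpaired samples". For continuous variables it continues: "Between-group differences at one time point will be evaluated by Wilcoxon-Mann-Whitney test (continuous variables"). Fisher's exact test covers categorical variables, and "All statistical tests are two-sided and statistical significance level alpha will be set at 0.05 for the analysis". No baseline term, covariate or between-arm comparison of change is mentioned.

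The Protocol Summary says of the primary and secondary endpoints: "Each of these parameters will be measured before trial initiation", and again after one month. It also describes a randomized study in which lycopene alone and plain dark chocolate serve as controls. The Protocol Summary and section 7.4.1 balance the groups on age and gender, and the Summary adds body weight and BMI. Section 13 uses none of these.

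Section 10.1 (Statistical effectiveness analysis) adds that if the listed methods do not suit the distribution of the results, "other methods of statistical analysis will be applied", with any deviation justified in an amendment and/or the final report.

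**The concern.** Two things are at stake. The first is precision. A comparison of month-1 values alone leaves all between-person variation in the error term, and with very small arms that is costly. The month-0 value is collected anyway and would remove part of that variation.

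The second is interpretation. A paired test within an arm has no concurrent control. All volunteers restrict cocoa and tomato products before and during the study, so a shift common to all arms is plausible. A before-after difference in one arm, or a significant result in one arm beside a non-significant one in another, does not estimate a product effect.

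This is not a detail left to an unseen analysis plan. The protocol names the tests, and section 10.1 treats them as the statistical plan.

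**Working it through.** **Inputs from the protocol**
- Total of 30 (Protocol Summary): "The study will be conducted following enrolment of 30 volunteers with equal representation in the study population of males and females".
- Five arms: the Summary and section 7.4.6 describe arms 1 to 5, for example "volunteers from the fifth arm will be given the regular formulation of DC without lycopene".
- Two-sided alpha of 0.05 (section 13).

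**Assumptions**
- Equal allocation, 30/5 = 6 per arm. No ratio is stated; section 7.4.1 says only "Randomization of volunteers in the study will be performed using widely accepted methods such as simple randomization and stratified randomization".
- SD = 1 at month 1, normal data, and month-0 to month-1 correlation r between 0 and 0.8. The protocol gives no effect size, SD, power or correlation, so its 30 cannot be reproduced.

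**1. Pairwise final-value comparison**

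Degrees of freedom: 6 + 6 − 2 = 10. Standard error: √(2/6) = 0.577 SD. From the noncentral t distribution:
- difference detectable with 80% power: 1.80 SD;
- power for a 1 SD difference: 35%.

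For the Mann-Whitney test that the protocol names, simulation (20,000 runs per setting) gives about 30% power for 1 SD.

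**2. One five-arm model with month-0 value and sex**

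Degrees of freedom: 30 − 5 − 1 − 1 = 23. Residual variance factor: 1 − r². Standard error: √(2(1 − r²)/6).

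| r | 1 − r² | Detectable difference, 80% power (SD) | Power for 1 SD |
|---|---|---|---|
| 0 | 1.00 | 1.69 | 38% |
| 0.3 | 0.91 | 1.61 | 41% |
| 0.5 | 0.75 | 1.46 | 48% |
| 0.7 | 0.51 | 1.21 | 64% |
| 0.8 | 0.36 | 1.01 | 79% |

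The r = 0 row separates two sources of gain. Moving from 1.80 to 1.69 SD (0.11) comes from pooling variance over five arms. At r = 0.5 the whole gain is 1.796 − 1.463 = 0.33 SD, so about one third is pooling and two thirds is baseline.

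The formula ignores chance imbalance in the month-0 means. A simulation that includes it, with baseline and arm but not sex (24 df), gives power of 40%, 47%, 63% and 78% at r = 0.3, 0.5, 0.7 and 0.8. Type I error is 4.8% to 5.3%.

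**3. Within-arm paired tests**

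The arms contain different volunteers, so five paired tests are independent. With no change in any arm, the chance of at least one significant result is 1 − 0.95⁵ = 0.226 per parameter.

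If all arms share a shift of 0.5 SD (assumed) and do not differ, simulation over r = 0.3 to 0.8 finds at least one arm significant in 52% to 88% of trials. Exactly one of arms 1 and 5 is significant in 23% to 45%.

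**The case against.** The strongest defence is that comparing final values between randomized arms is valid. It is only less efficient, and the protocol states no before-after claim. That stands, and it limits the severity.

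Four stronger readings are tempting, and the document does not support them.

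- **Change is examined only within arms, with two rival tests for one comparison.** Section 13 says only paired and unpaired. An unpaired t-test on change scores would fit those words, and a normality check followed by either a t-test or a rank test is the usual reading. The text is ambiguous. Month 0 against month 1 in the same volunteer is nevertheless the only natural pairing in this design. Change scores improve on final values only if r exceeds 0.5: the detectable difference is 2.12, 1.80, 1.39 and 1.14 SD at r = 0.3, 0.5, 0.7 and 0.8, in each case larger than with the adjusted model.
- **The test can be chosen freely once results are seen.** Section 10.1 allows a change only for distributional reasons and requires justification. The Protocol Summary also keeps the independent statistician unaware of group names and interventions. What remains is that the change may follow sight of the results, and its justification may appear only in the final report.
- **Most of the precision is lost.** Baseline removes r² of the variance: 9% at r = 0.3, 25% at 0.5, 49% at 0.7 and 64% at 0.8. Most holds only near the top of that range, and the protocol gives no r.
- **Two arms with the same true change will disagree half the time.** The chance is 2p(1 − p), where p is the power of one paired test, and 50% is its maximum. With n = 6 it is about 15%, 28%, 50%, 28% and 6% for a true change of 0.25, 0.5, 1, 1.5 and 2 SDs of change.

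**Conclusion.** The point holds as an efficiency and interpretation problem, and should be fixed. Section 13 fixes one-time-point between-arm tests and unspecified paired tests, and states no between-arm analysis that uses the month-0 value.

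With 6 per arm, an adjusted five-arm model lowers the detectable difference from 1.80 SD to between 1.61 and 1.01 SD for r from 0.3 to 0.8. Of this, 0.11 SD is due to pooling variance rather than to baseline. The size rests on equal allocation, roughly normal data on the analysis scale and an assumed r.

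The 22.6% for five within-arm tests needs only independent arms and valid 5% tests. That these paired tests are within-arm is an inference, though the natural one. A reader might conclude that the planned between-arm comparison is invalid; it is not.

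**What to change.** In section 13, for each continuous endpoint, make the efficacy analysis a linear model of the month-1 value on the month-0 value, sex and five-level arm, on a log or rank scale if the variable is skewed. Fit it to all randomized volunteers with data, a number that may differ from 30 because withdrawn volunteers are replaced. Report the between-arm contrasts with 95% confidence intervals.

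State that paired month-0 to month-1 changes within an arm are descriptive and support no claim of product effect.

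In section 10.1, require any change of method for distributional reasons to be documented before the group codes are broken.

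The cost is wording and two degrees of freedom (25 to 23 in the five-arm model). No further data are needed.

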a low bioavailability rate due to the hydrophobic nature of their amphiphilic molecules. Therefore, clinical studies aimed at the investigation of biological functions of lycopene and cocoa flavanols may require special nutraceutical formulations of these compounds with enhanced bioavailability. A newly developed lycosome formulation of DC (Lycotec Ltd, Cambridge, UK) contains both lycopene and cocoa flavanols in highly bioavailable forms (18). This formulation was developed by implementation of different microencapsulation techniques (spray drying, ultrasound, supercritical CO₂) which allows incorporation of bioactive compounds (lycopene and cocoa flavanols in this particular case) into the structure of lycosomes which are particles with an increased resistance to the acidic environment of the stomach and higher ability to be absorbed in the intestine (19). Besides the compounds of interest (lycopene and cocoa flavanols), lycosome particles (coco-somes) contain a phosphatidylcholine (used as a hydrophilizing and emulsifying agent).

Moreover, the lycopene used in lycosome-formulated DC is a well known antioxidant whose anti-radical capacities exceed the anti-radical capabilities of all other carotenoids multifold (20). Therefore, ingestion of lycosome-formulated DC may translate into significant attenuation of free radical formation in the human body. This creates the rationale to investigate parameters of biological oxidation in volunteers ingesting lycosome-formulated DC.

Altogether the factors mentioned above support the main objective of our study, creating a rationale for trying to investigate the effect of lycosome-formulated DC on microbiota spectrum and oxidation processes in healthy volunteers.

Each of these questions will be addressed in the current study.

7.3 Clinical Study Objectives:

7.3.1 Primary objective:

The primary objective of this clinical study is to verify the effect of lycosome-formulated dark chocolate (DC) and its two major ingredients – lycopene and cocoa flavanols on the spectrum of gut microbiota in healthy middle-aged overweight volunteers.

Secondary objective:

To investigate the effect of lycosome formulated dark chocolate (DC) and its two major ingredients – lycopene and cocoa flavanols on liver metabolism, blood lipids, marker of oxidative and inflammatory damage, and skin parameters in healthy middle-aged overweight volunteers.

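### The primary objective is the composition of the gut microbiota, but section 13 names only one-variable tests at unadjusted 0.05 and no composition measure or joint test

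*Protocol*

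**What the plan says.** Section 7.3.1 has one primary objective: the effect of the lycosome chocolate and its two ingredients "on the spectrum of gut microbiota in healthy middle-aged overweight volunteers". The summary in section 6 is wider: "the primary endpoint of the project will be parameters reflecting composition of gut microbiota, blood lipids and markers of serum levels of biological oxidation". Section 11.2 again takes the microbiota spectrum, with blood oxidation markers, as the measure of effectiveness.

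Section 13 (under 9.1, Study endpoint) lists the tests. Shapiro-Wilk is for checking normality. Then: "Student's t-test will be applied both for paired and unpaired samples". For comparisons between arms: "Between-group differences at one time point will be evaluated by Wilcoxon-Mann-Whitney test (continuous variables", with Fisher's exact test for categorical ones. The error rate is set once: "All statistical tests are two-sided and statistical significance level alpha will be set at 0.05 for the analysis".

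Section 10.1 allows other methods if the listed ones prove unsuitable to the new results because of how the values are distributed. Such deviations are to be justified in an amendment and/or the final report.

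The protocol does not say how the microbiota is quantified. Section 11 mentions only bacteriological analysis, and section 6 covers only collection, storage and shipment of the fecal samples.

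**The concern.** A microbiota spectrum is a profile of many quantities considered together. Every test in section 13 takes a single quantity, and the protocol names no diversity index, distance, log-ratio or other summary that would reduce the profile to one. What the plan gives on its primary objective is therefore a set of separate taxon comparisons, each at 0.05, with no stated rule for turning them into a conclusion about composition.

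Two things follow. The chance of at least one positive taxon when nothing has changed is high. And a modest shift spread over several taxa may show in none of them once the multiplicity is dealt with.

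A third problem depends on the data scale. If taxa are expressed as shares of a total, the shares sum to 100%, so a real rise in one taxon pushes the other shares down. A single-taxon test can then report a fall in a taxon whose absolute amount has not moved.

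**Working it through.** **Inputs.** From the protocol: 30 volunteers, five arms, two-sided 0.05, and the tests quoted above. Assumed: equal allocation, so 30/5 = 6 per arm (no ratio is stated), and 20 taxa unless noted (no number is stated). The target of 30 cannot be reproduced, because section 9.2 cites a pilot study without effect size, SD or power.

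**1. Multiplicity.** For k independent tests at 0.05, the chance of at least one false positive is 1 − 0.95^k:

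| k | 1 − 0.95^k |
|---|---|
| 5 | 23% |
| 10 | 40% |
| 20 | 64% |

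With 6 v 6 the exact Wilcoxon-Mann-Whitney test has an actual level of about 4%. For that test at k = 20 the figure is 1 − 0.96^20 = 56%.

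**2. Spill-over, if the data are shares.** Suppose one taxon changes and the absolute amounts of the others do not.
- A 30% share that doubles: the total becomes 0.30 × 2 + 0.70 = 1.30, so every other share is multiplied by 1/1.30 = 0.77.
- A 50% share that triples: the total becomes 0.50 × 3 + 0.50 = 2.00, so every other share halves.

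This was simulated with 6 v 6, 20 taxa and log-normal abundances (between-person SD 0.8, within-person SD 0.4 on the log scale). The rejection rate per unchanged taxon is:

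| Test | No change | 30% share doubles | 50% share triples |
|---|---|---|---|
| Wilcoxon-Mann-Whitney at the final time point | about 4% | about 6% | about 13% |
| Paired t-test within the arm | about 2.5% | about 6% | about 20% |

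**3. Sensitivity to the assumptions.** A second simulation applied the Wilcoxon-Mann-Whitney test to 10 taxa. The log-SD ran from 0.3 to 1.0, the changed taxon held 10% to 50% of the total, and its true rise was 2-fold or 4-fold. On shares, the rate per unchanged taxon ran from 4.3% (10% share, 2-fold, log-SD 1.0) to 96% (50% share, 4-fold, log-SD 0.3). A middle case (30% share, 2-fold, log-SD 0.5) gave 10%. On absolute counts the rate stayed at about 4% throughout, so there was no spill-over.

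**4. What a joint test would gain.** Setting: 6 v 6, 20 independent taxa, m of them shifted by 1 SD, values centred as a log-ratio transform requires. A full permutation test (924 splits) of the squared distance between arm means is compared with finding any taxon after Bonferroni. Bonferroni is a benchmark here; it is not in the plan.

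| Taxa shifted | Global test | Any taxon, Bonferroni |
|---|---|---|
| 5 | about 44% | about 17% |
| 10 | about 61% | about 19% |

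With one shifted taxon the advantage almost disappears (about 13% v 10%). With taxa in four correlated blocks (correlation 0.5) it narrows to about 31% v 18% for 5 taxa and 42% v 20% for 10.

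**The case against.** **The endpoint is plural.** Section 6 speaks of parameters reflecting composition. A named genus, a ratio or a diversity index could each go through a listed test. This stands against the stronger reading that composition is never tested, or that the trial cannot answer its primary question. A reader might infer that from the list of tests, but the documents do not support it. What they show is that no such parameter is named.

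**This belongs in the statistical analysis plan.** Transforms and distance measures often do go there, and section 13 does not say that only its tests may be used. But the protocol lists its tests, sets alpha and, in section 10.1, treats that list as the plan from which departures must be justified. The point concerns a stated choice that does not match the objective.

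**Section 10.1 allows other methods.** It does, but the trigger is the distribution of results already obtained. That the endpoint is a profile is known now. A composition test brought in by this route would be chosen after seeing the data.

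**Spill-over is conjecture.** It is conditional. A reader might assume relative abundances because the objective speaks of a spectrum, but no assay or scale is stated. On absolute counts only the multiplicity remains.

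**Larger figures are possible.** A between-arm test of log change gives 30% and 9% on unchanged taxa, but section 13 does not name that test. Power of 57% and 91% for the global test comes from uncentred values, in which some taxa rise and none fall. That pattern cannot occur on a centred log-ratio scale. Neither set of figures should be used.

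**Conclusion.** The point holds in limited form. The primary target is composition, the named tests are all univariate at unadjusted 0.05, and neither a composition measure nor a joint test is prespecified. The 64% for 20 taxa assumes independence and exact 5% tests; it would be lower with correlated taxa and is about 56% at the Wilcoxon-Mann-Whitney test's actual level.

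The spill-over applies only to relative abundances. In the main scenarios it is small to moderate, and it depends heavily on the share, the size of the change and the spread. The gain from a joint test is real if several taxa shift, but power stays modest with an assumed 6 per arm. The plan should be changed, and the change is cheap. The protocol does not show that the primary question is unanswerable.

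**What to change.** In section 13:

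1. State the microbiota assay and whether results are relative abundances or absolute counts.
2. Prespecify one primary microbiota analysis. One suitable choice is a permutation test of the between-arm difference in within-person change of the profile, log-ratio-transformed if the data are relative and on log counts if they are absolute. Test arm 1 v arm 5 first, since section 6 uses that contrast to assess the lycosome chocolate. A single named composition index with a matching between-arm test would also close the gap.
3. Make single-taxon tests secondary and descriptive, and run them on log-ratio values if the data are relative.

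The cost is protocol or analysis-plan wording and a little more analysis, with no new samples or visits. The drawback is that a global test does not say which taxon moved, so the single-taxon results are still needed as description.

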Fecal specimens will be collected at the same time points by volunteers in the comfort of their homes and will be required to be delivered to the study laboratory within 1 hour of collection. All fecal specimens will be frozen and stored at the study site until analysed. Should any shipping be required the study specimens will be shipped on dry ice by overnight courier.

Among the biochemical tests conducted on serum specimens will be the activity of liver specific enzymes (alanine aminotransferase and aspartate aminotransferase as well as activity of gamma-glutamyltransferase), level of bilirubin, concentrations of triglycerides, LDL, HDL, total cholesterol and levels of peroxidation products (IOD and LDL-Px).

Biochemical assays will be performed by qualified and licensed personnel using a BioSystems Analyzer and compatible commercial kits of reagents. Standards will be purchased from Sigma-Aldrich only.

Skin swab parameters will be assessed on sebum quantity and viscosity, rate of corneocyte desquamation and damage, and total bacterial load of gram-negative bacteria.

[figure not shown]
Encoding of the results will be performed in collaboration with the Principal Investigator and the Medical Monitor.

[figure not shown]
Statistical analysis will be performed by an independent statistician using commercially available “BioStat-3” software. The statistician will not be informed of study group names or the nature of interventions in each group.

Packaging and labeling of study products and biological specimens will be carried out according to the guidelines of the NIH and US Department of Health and Human Services, as recommended for biologicals and investigational health food products. The study products will be shipped to the study site in specially designed containers with primary and secondary components. A container closure system will be used to avoid contact of investigational products with light, moisture, excess temperature and air. This packaging system guarantees stability of the products for the intended use. Protection from microbial contamination is provided by maintaining container integrity after the packaging system has been sealed. An adequate and validated procedure will be used for investigational product manufacture and packaging.

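### Every test is judged at an unadjusted 0.05 across five arms and an open, inconsistent primary endpoint, so the chance of a false positive claim is several times 5%

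*Protocol*

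**What the plan says.** **Error rate.** Section 13 (9.1 Study endpoint): "All statistical tests are two-sided and statistical significance level alpha will be set at 0.05 for the analysis". No adjustment, testing order or overall five-arm test is given.

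**Tests.** The same section states: "Student's t-test will be applied both for paired and unpaired samples". It assigns between-group differences at one time point to the Wilcoxon-Mann-Whitney test, or to Fisher's exact test for categorical variables. Between arms, all of these are used as two-group tests. The paired t-test compares an arm with itself.

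**Arms and size.** The Protocol Summary and Section 7.4.6 describe five arms. Arm 1 receives the lycosome chocolate, "while volunteers from the fifth arm will be given the regular formulation of DC without lycopene". Arm 2 receives lycopene capsules matched to arm 1's lycopene content. For the remaining two: "To assess dose-dependency and effect of fat matrix volunteers from the third and fourth arms will be given 30 mg of lycopene", in different fats. The total is given as "Sample Target Size: 30", with no allocation ratio.

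**Primary endpoint.** The Protocol Summary lists microbiota composition, blood lipids and serum oxidation markers as primary. It names two of those markers and leaves the rest of the list open. Section 7.3.1 confines the primary objective to the microbiota and makes lipids and oxidation markers secondary. Section 11.2 takes microbiota and oxidation markers as the effectiveness measures and omits lipids.

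**Blinding.** Of the analyst, the Protocol Summary says: "The statistician will not be informed of study group names or the nature of interventions in each group".

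**The concern.** A 5% level limits false positives for one test. Here it applies to each of many tests, and nothing says which test decides the trial. Several variables are primary, the list is not closed, two sections disagree about it, and any pair of arms could be reported as the result. If one of these tests gave p below 0.05, a reader could not tell it from a chance finding.

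Two features make this worse. Section 10.1 allows other methods once results are in hand, with the explanation given as late as the final report. And with about six people per arm, a blanket correction applied afterwards may leave the rank test unable to reject at all. The problem is therefore hard to repair after the data are seen.

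**Working it through.** The protocol states no familywise error rate or power, so it has no figure to reproduce. Its only error figure is the 0.05.

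**Inputs**
- Arms: 5 (Protocol Summary; Section 7.4.6). Possible pairs: 5 × 4 / 2 = 10. Pairs involving arm 1: 4.
- Per arm: 30 / 5 = 6. Equal allocation is an assumption.
- Variables that can be counted: 4 lipids (total cholesterol, LDL, HDL and triglycerides, from the list of serum tests in the Protocol Summary), 2 named oxidation markers, and the microbiota taken as 1 summary. 4 + 2 + 1 = 7. The true number is not fixed.
- Tests: 7 × 10 = 70 over all pairs; 7 × 4 = 28 for arm 1 against the others.

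**Size of one exact rank test at 6 versus 6.** There are C(12,6) = 924 arrangements. The smallest two-sided p is 2/924 = 0.0022. The largest attainable p below 0.05 is 38/924 = 0.0411, so each test has a true size of 4.1%. With no true effects, the expected number of false positives is 70 × 0.0411 = 2.9 over all pairs, or 28 × 0.0411 = 1.2 for arm 1 only, whatever the correlation.

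**Independence formula, for reference.** 1 − 0.95^10 = 0.40, 1 − 0.95^28 = 0.76 and 1 − 0.95^70 = 0.97. These overstate the rate, because pairs share arms and variables are measured on the same people. The figures below are therefore simulated.

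**Simulation.** Five arms of 6, no true effects, normal data, equal correlation between variables, 6,000 to 10,000 runs. Chance of at least one p below 0.05 between arms:

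| Variables | Comparisons | Correlation | Exact Mann-Whitney | t-test |
|---|---|---|---|---|
| 1 | all 10 pairs | – | 0.25 | 0.29 |
| 7 | arm 1 v others | 0 | 0.62–0.64 | 0.69–0.70 |
| 7 | arm 1 v others | 0.5 | 0.53–0.55 | 0.58–0.60 |
| 7 | arm 1 v others | 0.8 | 0.39 | 0.42 |
| 7 | all 10 pairs | 0 | 0.87–0.88 | 0.91 |
| 7 | all 10 pairs | 0.5 | 0.78–0.80 | 0.81–0.83 |
| 7 | all 10 pairs | 0.8 | 0.61–0.62 | 0.64 |

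Where two values are shown, separate runs differed by a point or two. A hand check at zero correlation agrees: the one-variable rate for arm 1 against the others is about 0.13, and 1 − 0.87^7 = 0.62. For all pairs, 1 − 0.75^7 = 0.87.

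**Adding the paired tests.** Five within-arm t-tests per variable, on top of all pairs by Mann-Whitney on final values, give 0.97, 0.94 and 0.84 at correlations 0, 0.5 and 0.8. This assumes a baseline-to-final correlation of 0.5.

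**A late Bonferroni correction.** The largest number of tests for which the exact rank test can still reject is 0.05 / 0.00216 = 23.1, so 23. For 28 tests the threshold is 0.05 / 28 = 0.0018, and for 70 it is 0.05 / 70 = 0.0007. Both lie below the smallest attainable p of 0.0022.

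**The case against.** **A statistical analysis plan, not at hand, may settle multiplicity.** It may, and silence alone would be no finding. But the protocol is not silent. It sets 0.05 for all statistical tests, and Section 10.1 refers to this text as the statistical plan. The open and contradictory primary endpoint is also a protocol matter.

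**Ten comparisons are possible, not planned.** This stands. No section says that all pairs will be tested. The Protocol Summary places the effects of lycopene alone and of plain chocolate among the secondary objectives, and it gives each arm a purpose. That suggests a hierarchy, which is why the arm 1 comparisons are shown separately. It does not name a primary contrast, and even the narrower set gives 39% or more for seven variables.

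**The seven variables are a construction.** This also stands. If Section 7.3.1 governs and one microbiota summary is used, the all-pairs rate is 25 to 29%. That is still five to six times the stated level.

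**Stronger readings that the protocol does not support**
- *A false positive on the primary endpoint is close to certain.* For the between-arm tests that can be counted, the rate tops out near 90%. Reaching about 95% or more takes added assumptions: the paired tests at low correlation, or some 20 variables over all pairs with correlation up to about 0.5. The protocol gives no count of taxa and does not mention taxon-level testing.
- *A blinded statistician can only test every pair.* The protocol withholds group names and interventions. It does not rule out a coded list of contrasts.
- *No correction could ever work.* The floor of 0.0022 belongs to the exact rank test at 6 versus 6. The unpaired t-test, also named in Section 13, has no such floor.

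**Conclusion.** The point holds as a matter of size, not of certainty. Section 13 fixes an unadjusted two-sided 0.05 for every test, while the primary variable and the primary contrast are left open and two sections disagree on what is primary. With equal allocation, no true effects and the exact Mann-Whitney test, the chance of at least one false positive between arms is about:

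- 25% for one variable over all pairs (29% with the t-test);
- 39 to 62% for seven variables when only arm 1 is compared with the others;
- 61 to 88% for seven variables over all pairs.

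The ranges run from a between-variable correlation of 0.8 down to 0. Every scenario is far above 5%. The exact figure cannot be known, because the protocol fixes neither the number of variables nor the comparisons.

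**What to change.** 1. Reconcile the Protocol Summary with Section 7.3.1 so that one defined microbiota measure is the primary endpoint. No such single measure exists in the protocol yet, so objectives and endpoints must be edited as well as Section 13.
2. Before unblinding, name one confirmatory contrast on that measure at two-sided 0.05. Arm 1 versus arm 5 fits the purpose that the Protocol Summary gives those arms. Another contrast could be defended, provided it is fixed in advance.
3. Only if that test succeeds, test arm 1 versus arm 2 on the same measure at 0.05. The fixed order keeps the overall error of the pair at 5%.
4. Report all other contrasts and endpoints, including the within-arm changes, as exploratory estimates with 95% confidence intervals. Apply false discovery rate control (Benjamini-Hochberg) to any taxon-level tests.
5. Give the statistician the contrasts in coded form, for example A versus E, so that blinding is kept.

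The cost is wording only, with no new data or participants. The downside is that most comparisons can no longer be claimed as statistically significant findings.
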